Yeager and colleagues have developed brief interventions aimed to change entity theories by means of efficient and persuasive intervention tactics that are based on the above mentioned mechanisms. For instance, in one of these interventions, a six-session high school classroom intervention teaching an incremental theory reduced aggressive behavior by 40%, improved depressive symptoms two weeks post-intervention, and increased school attendance (Yeager, Trzesniewski, & Dweck, 2013). Later, they tested the effects of a shorter intervention consisting of only one session. This single session touch an incremental theory via computers. In this session 9th grade students read a scientific article about the possibility of personality change, then they read quotes from older students transmitting the same message. Finally, the students

wrote a brief essay where they defended the same idea with the aim of transmitting the message to other students in the future. Despite the brevity of this intervention, the results obtained by means of a double-blind randomized experiment showed that it reduced levels of self-reported clinically relevant depression (Miu & Yeager, 2014) and stress levels (Yeager et al., 2014).

II. AIMS AND HYPOTHESES

Aim 1: To replicate the effect of an intervention based on Implicit Theories of Personality (ITP) on depressive symptoms (Study 1) and aggressive behavior (Study 2) in a large sample of Spanish adolescents. Grounded on the previous findings obtained in US samples, we will test the efficacy of the ITP intervention by comparing changes in depressive symptoms and aggressive behavior from pretreatment to follow up between the group receiving the ITP intervention and a control group that will receive a control educational condition.

Hypothesis: Those adolescents receiving the ITP intervention will show fewer symptoms of depression and lower frequency of aggressive behavior than the control group after the intervention and at six-month and one-year follow-up.

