building on a long line of research on cognitive dissonance (Walton & Cohen, 2011). For a more complete description of the ITP intervention see Yeager et al. (2013). The intervention will be adapted to the developmental characteristics of the participants.

The **educational intervention** involves scientific information about the human brain. It was designed to be parallel to the experimental intervention and, hence, it has also three main parts. First, participants are asked to read scientific information about the different areas of the brain and their specialties. Second, participants read several testimonials written by upperclassmen about their transition to high school and how their brains help them to adapt to the new space and all the physical differences of the building and the classes. Finally, participants are asked to write a letter to another student explaining the main things he or she has learned about the brain and thinks are important for adapting to the new physical environment in high school. Hence it will control for the possibility that simple optimism about the potential for growth might account for our results. This is a conservative control group. An entity theory control group would be unethical in a longitudinal field experiment because it could teach the belief that personality cannot be changed, which has been associated to negative consequences.

Procedure

Parental informed consent forms will be sent to parents and adolescents. Those who accept to participate in the study will complete report measures at four waves: (1) one-week before intervention; (2) one-week after intervention; (3) six-months follow-up; and (3) one-year follow-up. Saliva samples will be collected at the same time points. Parents' participants will complete report measures at three waves: (1) one-week before intervention; (2) six-months follow-up; and (3) one-year follow-up. Intervention will be applied one week after the first survey. All the measures will be anonymous and participants will be asked to provide certain data (her/his birth date, first initial of mother's name, and first initial of father's name) to match their questionnaires, saliva samples and intervention tasks over time. Both interventions and assessment measures will be administered by research assistants during normal class time and last around 50 minutes.

Ethical considerations

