This study aims to develop and implement interventions that will be beneficial for the participating adolescents and other people in the future, by helping to increase their psychological wellbeing. Through randomization, the principle of justice will be respected, allowing all participants to have similar opportunities to receive the intervention. Gender will be considered and similar number of male and female participants will be included in the studies.

The risks are minimal and limited to answering psychological tests on stressors, psychological symptoms and cognitive styles. Previous experience with the same

questionnaires indicates that the risk is minimal. Adolescents can also decide to end their participation at any moment. Researchers collecting data will be trained to attend to any difficulty that could emerge while participants are responding to questionnaires. The researchers will give an alternative task (e.g., educational readings) to those participants who decide to end their participation.

Informed consent forms will be sent to parents or legal guardians to complete. Adolescents will also receive written information. The active consent of parents or legal guardians and of adolescents will be necessary for participation in the project. We will incentive adolescents for bringing parent forms, even when decision is negative.

Parents will be invited to complete measures of children's temperament and send their completed questionnaires in a stamped envelope that will be provided without any identifying information. Adolescents will complete the measures in the classroom. Saliva samples and their analysis will be processed according to existing regulations in a professional lab.

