After completing measures, adolescents will be provided with information on services for adolescents (e.g., phone number of attention to adolescents). From an ethical perspective, the most important care aspect is the protection of information. We will follow the Directive 95/46/EC of the European Parliament, *Ley Orgánica 15/99 de 13 de diciembre de Protección de datos de Carácter Personal*, and of the Council of 24 October 1995 on the protection of individuals with regard to the processing of personal data and the free movement of such data. No identification data, such as names or surnames, will be used; instead, we will use a numeric code to match measures across times and sources (parents, and adolescents). Thus, each adolescent, and only he/she, will know his/her code. We will also follow the procedure for data protection that the University of Deusto has registered in the National Data Protection Agency. The project has been approved by the Ethics in Research committee of University of Deusto.

IV. STATISTICAL ANALYSES PLAN

Descriptive statistics of sociodemographic and study variables will be provided and several statistical strategies will be used to test the hypotheses. These will include mixed analyses of variance (ANOVA), multilevel analyses, regression analyses, among others. We will use IBM SPSS, MPLUS, LISREL, and HLM software for analyses.

References

Achenbach, T. M. (1991). Child Behavior Checklist/4-18 and 1991 profile. *Burlington, Vermont, USA: University of Vermont, Department of Psychiatry*.

Achenbach, T. M., & Edelbrock, C. S. (1983). Manual for the Child Behavior Checklist/4-18 and revised child behavior profile. *Burlington, Vermont, USA: University of Vermont, Department of Psychiatry*.

Blackwell, L. S., Trzesniewski, K. H., & Dweck, C. S. (2007). Implicit theories of intelligence predict achievement across an adolescent transition: A longitudinal study and an intervention. *Child Development*, 78(1), 246-263. doi:10.1111/j.1467-8624.2007.00995.x

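### The plan names no primary model, follow-up, analysis set or missing-data rule for the pupil outcomes, and the change comparison stated in Aim 1 is less precise than a baseline-adjusted one

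*Combined protocol and SAP*

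**What the plan says.** Section IV (Statistical analyses plan) has three sentences. The first promises descriptive statistics and several strategies for testing the hypotheses. The second lists them: "These will include mixed analyses of variance (ANOVA), multilevel analyses, regression analyses, among others". The third names four software packages. No method is tied to an aim, an outcome or a set of waves.

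In section II, Aim 1 is to be tested by "comparing changes in depressive symptoms and aggressive behavior from pretreatment to follow up". Its hypothesis is that the ITP group will do better "than the control group after the intervention and at six-month and one-year follow-up". That makes three follow-ups, none of them marked as primary.

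Section III, Procedure: "Those who accept to participate in the study will complete report measures at four waves". Pupils supply personal data "to match their questionnaires, saliva samples and intervention tasks over time". Under Ethical considerations: "Adolescents can also decide to end their participation at any moment"; "Adolescents will complete the measures in the classroom"; and, on linkage, "Thus, each adolescent, and only he/she, will know his/her code".

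No section gives a missing-data rule for pupil outcomes. The nearest text, under Measures, concerns parent reports: they will be used if the response rate suffices, and no threshold is set.

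**The concern.** There are two consequences.

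First, several methods and three follow-ups are open, so which result counts as the test of Aim 1 can be settled after the results are known. A significance level quoted for the reported result would then not be the true error rate.

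Second, the only comparison that the documents describe is one of changes from pretreatment. In a randomised trial, adjusting the follow-up score for baseline estimates the same effect with less variance, and it needs no extra data.

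Missing waves make the silence matter more. They are foreseeable: pupils may withdraw at any time, measures are taken in class over a year, and records are joined through data and a code that the pupil supplies. The plan does not say what happens to a pupil with a partial record.

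**Working it through.** **Inputs from the documents.** About 900 pupils, allocated 1:1 (450 per arm), individually within classroom and blocked by gender (section III, Study design and participants). Four waves, of which three are follow-ups. The documents give no effect size, significance level, power, baseline correlation or attrition rate, so there is no figure of the plan's own to reproduce.

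**Assumptions.** Effect 0.20 SD; two-sided 5%; equal variance at each wave (SD = 1); correlation r between baseline and follow-up of 0.4, 0.55 or 0.7; absence at random. Clustering is not modelled.

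**1. Change against baseline adjustment.**

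- Variance factor for change: v = 2(1 − r).
- Variance factor for baseline-adjusted: v = 1 − r².
- Ratio: 2(1 − r)/(1 − r²) = 2/(1 + r). The difference is (1 − r)², so adjustment does not lose in large samples, whatever the attrition.
- SE = 2√(v/n); power = Φ(0.20/SE − 1.96).

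Example with r = 0.55 and n = 855:

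- Change: SE = 2√(0.90/855) = 0.0649; 0.20/0.0649 = 3.08; power Φ(1.12) = 0.87.
- Adjusted: SE = 2√(0.6975/855) = 0.0571; 0.20/0.0571 = 3.50; power Φ(1.54) = 0.94.

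| r | v, change | v, adjusted | ratio | power, change (n = 855 to 873) | power, adjusted |
|---|---|---|---|---|---|
| 0.4 | 1.20 | 0.84 | 1.43 | 0.76–0.77 | 0.89–0.90 |
| 0.55 | 0.90 | 0.6975 | 1.29 | 0.87–0.88 | 0.94 |
| 0.7 | 0.60 | 0.51 | 1.18 | 0.97 | 0.98–0.99 |

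The sizes 873 and 855 are 900 less an assumed 3% and 5% absent at one week.

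**2. The open choice.** A simulation with no true effect (n = 900, r = 0.55, nested absence of 5/10/20% at the three follow-ups, 2,000 replicates) compared three analyses: change in completers, change in all observed pupils, and baseline-adjusted.

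| What may be reported | Significant at 5% |
|---|---|
| One named analysis at one year | 5.3% |
| Any of the three analyses at one year | 7.6% |
| One analysis at any of three follow-ups | 14% |
| Any of the nine | 21% |

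Most of the inflation comes from the unnamed follow-up. This is for one outcome and shows what the text permits. It does not suggest intent.

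**3. Hypothetical illustration: listwise four-wave ANOVA.** Suppose that a mixed ANOVA over all four waves, keeping only pupils with every wave, were the reported result. Complete pupils are 900 × (1 − one-year absence) if absence is nested, and 900 × the product of the three presence rates if it is independent. The SE ratio is √(observed/complete).

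| Assumed absence (1 week / 6 months / 1 year) | Observed | Complete, nested | SE ratio, nested | Complete, independent | SE ratio, independent |
|---|---|---|---|---|---|
| 3/8/15% | 873/828/765 | 765 | 1.07/1.04/1.00 | 683 | 1.13/1.10/1.06 |
| 5/10/20% | 855/810/720 | 720 | 1.09/1.06/1.00 | 616 | 1.18/1.15/1.08 |
| 5/15/30% | 855/765/630 | 630 | 1.17/1.10/1.00 | 509 | 1.30/1.23/1.11 |

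At r = 0.55 and nested absence, one-week power for change in completers is 0.83, 0.81 and 0.75, against 0.87 to 0.88 for change in all observed pupils.

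**The case against.** The strongest reply is that the plan commits to nothing wasteful. A reader might infer from the words mixed ANOVA that partial records will be thrown away. The documents do not say so. They do not put four waves in one ANOVA, mention listwise deletion, assign ANOVA to Aim 1, or prefer it to the multilevel analyses in the same sentence. The list serves four aims, and a two-wave ANOVA for each follow-up would lose less. This objection stands, and it is why step 3 is only an illustration.

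Further objections limit that illustration:

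- Under nested withdrawal nothing is lost at one year.
- Fully independent absence is a near-worst case. Absence that clusters within pupils moves the counts towards the nested column.
- The usual group-by-wave test has three degrees of freedom. With the same effect at each follow-up, its completers power is 0.86, 0.84 and 0.78, slightly above the one-week contrast. A contrast of mean follow-up against baseline reaches 0.95, 0.93 and 0.90.
- Not every failed link is recoverable. Intervention tasks are matched by the same self-supplied data, so if that link fails and no other allocation record exists, the arm is unknown and no model restores the pupil.

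A reader might also infer bias. Under random absence, completers give an unbiased estimate. In one simulated mechanism, with dropout depending on the one-week score in the control arm only, the listwise one-week effect was −0.141 against a true −0.2, while the one-year contrast was unbiased (−0.202). Bias is thus possible, but nothing in the documents shows that it will occur.

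Finally, the listed regression analyses could include baseline adjustment. They could, but the plan does not say so, and Aim 1 speaks of changes.

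**Conclusion.** The point holds as an open choice of result together with an inefficient stated comparison. The absence of a primary model, follow-up, analysis set and missing-data rule for pupil outcomes is certain from the text. The precision cost of comparing changes is a variance 1.18 to 1.43 times that of the adjusted comparison. At r = 0.55 and 0.20 SD this is about 7 points of power (0.87–0.88 against 0.94). It rests on assumed correlations and equal variances, and not on attrition.

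The loss from discarding partial records is conditional on an analysis that the plan allows but does not state. With an assumed nested loss of 15 to 30% by one year, SEs would be 7 to 17% larger at one week, 4 to 10% larger at six months, and no larger at one year. The 13 to 30% at one week under independent absence is an upper illustration.

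It would also go too far to say that the right model is already in the plan. Multilevel analyses are listed without an estimator, and without saying that waves are a level. They could mean only pupils within classrooms.

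The plan should be changed on this point. Confidence is high on the omission and moderate on its size.

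**What to change.** For each study, name one primary efficacy model, taken from the listed multilevel analyses and specified as follows:

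- likelihood estimation, with waves nested in pupils;
- all randomised adolescents in their allocated arm, and all observed waves;
- arm-by-wave terms;
- baseline, either as a covariate or as a first wave with a common mean in both arms;
- sex (the blocking factor) and classroom/school.

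Name one follow-up contrast as primary, for example one year, and report the other two as secondary. Keep mixed ANOVA as a secondary completers analysis.

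State that the primary model assumes data missing at random, and add one simple sensitivity analysis. An example is multiple imputation with missing ITP-arm scores shifted towards worse. The shift sizes are for the sponsor to justify.

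The cost is SAP wording and one extra analysis. HLM and Mplus are already planned, and no further pupils, visits or data are needed. The small downside is reliance on the missing-at-random assumption. If one year is made primary and absence is nested, the gain there over a completers change comparison comes from baseline adjustment and not from recovered records: with 765, 720 and 630 pupils at r = 0.55, power rises from 0.83, 0.81 and 0.75 to 0.91, 0.90 (0.895 before rounding) and 0.85.
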